Refining the Shared Decision Making Process Survey in ADHD Medication Decisions

Protocol and analysis plan

PI: [name]

Statistician: [name]

Clinical Trials.gov: NCT05048186

IRB at Mass General Brigham: # 2019P001434

Funding: R01HS025718 from the Agency for Healthcare Research and Quality (AHRQ)

Co-Investigators and Study team: [name] (Massachusetts General Hospital (MGH), Harvard Medical School (HMS)), [name] (Center for Survey Research, University of Massachusetts Boston), [name] (Cincinnati Children's Hospital), [name] (MGH), [name] (MGH, HMS), [name] (MGH)

Website: www.mghdecisionsciences.org

Contact: [name] [contact]

Document Date: August 10, 2023

Background: Shared decision making (SDM) is recommended for common pediatric conditions; however, there is limited data on measures of SDM in pediatrics. This study adapted the SDM Process scale and examined validity and reliability of the scale for ADHD treatment decisions.

Purpose: The primary purpose is to examine the performance of the SDM Process scale for pediatric medical decisions. A secondary purpose is to evaluate the impact of a Decision Aid on participant knowledge of ADHD treatment options.

Design: Retrospective observation study of parents who had recently made a decision about medication for their child's ADHD. We worked with a national sampling firm to obtain a target of 500 responses. The sampling firm sent an email invitation to potentially eligible panel members informing them that a survey is available for which they are eligible. Respondents choose to participate or not. The sampling firm's database does not hold sensitive or confidential panelist information. The firm stopped emailing web panel members once they received 500 completed surveys. The study investigators received de-identified participant information from the firm and did not have access to participants' emails or any of their personal information.

After completing the main decision making surveys, participants in the sample will be randomized 1:1 to one of two arms. Participants in the intervention arm will review a Decision Aid (patient educational tool) partway through the survey and those in the control arm will not receive any educational materials.

Sample: Participants were caregivers (n=498) of children (aged 5-13) diagnosed with ADHD, who had made a decision about ADHD medication in the last 2 years. The sample was not a national probability sample; however, the recruitment efforts were managed to be geographically diverse and to have at least 25% non-White respondents.

Intervention: Intervention arm received the Behavioral Attention Deficit Hyperactivity Disorder Treatment Decision Aid presenting benefits and harms of different treatments for ADHD. The decision aid was created at Cincinnati Children's Hospital.

The control arm did not receive any materials.

Survey protocol: The online survey was fielded between February 2021 and March 2021. Participants completed screener questions to determine eligibility. Then, they reviewed an information sheet that described the study and had to acknowledge that they read it and were willing to continue to the survey. Then, they continued to the survey. They were asked to identify the main decision they made about ADHD medicine over the past two years (“In the last 2 years, what was the main decision you made about using medicine to treat your child’s ADHD?”; see Table 1) and were instructed to respond to the rest of the items thinking about that main decision.

All participants completed surveys before viewing the decision aid including the SDM Process scale Pediatric version (scores range 0-4, higher scores indicate more SDM), decisional conflict, decision regret, and decision involvement. Participants in the intervention arm completed the knowledge survey after reviewing the decision aid.

Starting 7 days after they completed the survey, respondents were invited to complete a brief follow-up survey to examine short term test-retest reliability. The goal of the retest was to obtain 200 completed surveys. Consent was implied by completion of the survey.

Risks and Adverse Events: No diagnosis or treatments were offered or administered as part of this study. The standard of care is that physicians discuss appropriate treatment options, including their benefits and risks with the caregiver and child. There are minimal risks associated with participating in the online field. The respondents to the online panel have already given permission to be contacted by signing up for the panel. The participants in the online panel may stop their participation at any time. No confidential or PHI was collected as part of this study.

There are no adverse events expected for this minimal risk survey study. Study staff will review the completed data set and will notify the site PI about any serious or moderate potential adverse events (AEs) immediately and any minor or potential ones at weekly meetings. The PI will review AEs individually real-time and in aggregate on a weekly, basis at team meetings. The PI and clinician co-investigators will review potentially serious adverse events (SAEs), as soon as

they are discovered. The PI ensures all protocol deviations, AEs, and SAEs are reported to the IRB according to the standard requirements.

There are no formal stopping rules for this minimal risk study.

Outcomes: The survey collected the following information:

- *SDM Process scale pediatric version (administered before the decision aid):* Four items cover discussion of options, pros, cons, and preferences.¹⁴ The items measures whether or not a specific behavior had occurred during an interaction with a healthcare provider about the treatment decision (see Table 2 for all items). Items were scored and summed in accordance with previously published work and a total score between 0 and 4 was calculated.¹⁴ Higher scores indicate more SDM occurred. Participants with missing answers were not given a Pediatric SDM Process score.
- *Decisional Conflict (administered before the decision aid):* The SURE scale is the 4-item short form of the Decisional Conflict Scale that measures the level of uncertainty about which treatment to choose. Each item is scored as “Yes” (1 point) or “No” (0 points) with total scores ranging from 0-4. A total score of 4 indicates no decisional conflict.^{15,16} SURE has been shown to correlate positively with the SDM Process score in a range of surgical decisions,¹⁴ as well as for decisions surrounding medication to manage depression.¹⁷ The longer Decisional Conflict scale has been used to measure decisional conflict both in surrogate decision makers,¹⁸ as well as in pediatric populations.¹⁹

- *Decision Regret (administered before the decision aid)*: 1 item assessed whether or not respondents would make the same decision again. Response options were on a scale from 1 (definitely make same decision again) to 4 (definitely NOT make same decision again). This item has not been used in pediatric studies, but has been used in previous studies by the authors and has been shown to be inversely related to the SDM Process scores for surgical decisions.¹⁴
- *Modified Control Preferences Scale (administered before the decision aid)*: 1-item, modified by the researchers and used in prior work,²⁰ asking who made the decision, with response options: “Mainly you”, “Mainly your child’s healthcare provider”, “You and the healthcare provider made the decision together”, and “Mainly someone else”.²¹ This version has not yet been used in a pediatric context, however the original Control Preference Scale been used in pediatric contexts.^{22,23}
- *Knowledge (administered after the decision aid)*: 7 multiple choice knowledge items that covered options, benefits and harms of medication and other treatments for ADHD. A total score (0-7) was created and converted to a 0-100% scale. Higher scores indicated higher knowledge.
- *ADHD severity* : Parent Informant Performance subscale of the National Institute for Children’s Health Quality (NICHQ) Vanderbilt Assessment Scales.²⁴ Score range from 8 to 40 with higher scores indicating more problematic behavior.

- *Demographic and other information:* Participants were also asked to report on demographic information, current ADHD treatment(s), prior AHDH treatment(s), and years with ADHD.

Sample Size: The sample size was determined to ensure sufficient power to detect differences in knowledge by DA exposure of about 0.25SD at 0.05 significance with 80% power would require 250 per group.

Statistical methods: First, we examined descriptive results for the main decision item, the SDM Process scale, knowledge and other outcomes.

For the SDM Process scale, we also looked to see whether the scores spanned the range of total possible scores, were normally distributed, and whether there was evidence of floor or ceiling effects. Using a one-way ANOVA we tested for differences in Pediatric SDM Process scores by main decisions.

Then we examined the convergent validity and reliability of the SDM Process scale. As there is no gold-standard for measuring SDM, we tested the following hypotheses to examine validity of the scales by looking at relationships between known constructs such as decision conflict and decision regret.

Validity Hypotheses

1. Patients with higher Pediatric SDM Process scores ($\geq .33SD$) were more likely to receive a top-score SURE score.
2. Patients with higher Pediatric SDM Process scores had less regret ($r \geq -.50$).
3. Respondents who reported that their decision making process was mainly driven by the physician had lower Pediatric SDM Process scores ($\geq .33SD$) than respondents who reported that they were involved and engaged in selecting treatment.

For hypothesis 1, we compared mean Pediatric SDM Process scores for those who were SURE (score=4) and those who were not (score <4) with a Welch's 2-sample t-test since Pediatric SDM Process scores showed significant heterogeneity when examined for SURE groups. For hypothesis 2, we used a Pearson's correlation to determine the relationship between Pediatric SDM Process and regret. ANOVA determined if there were differences in Pediatric SDM Process scores by who made the decision.

We assessed retest reliability using Intraclass correlation coefficient (ICC; $ICC > 0.7$ indicating sufficient reliability).²⁵

We examined individual knowledge items for % correct and % missing data. We calculated a total knowledge score and looked to see whether the scores spanned the range of total possible scores, were normally distributed, and whether there was evidence of floor or ceiling effects. We ran r point-biserial correlations of individual items with the total knowledge score. We then compared knowledge scores between arms using two sample t-test.

Data Sharing: We are committed to making resources and data from the proposed research available to other investigators in the research community. The data collected in the online field test will be made available to others for analysis and research. The study team will create a complete, cleaned, de-identified copy of the final data set. Information for investigators interested in using this data will be made available on the Health Decision Sciences Center website and in publications of the data. [name] will share a de-identified data set with outside investigators at no cost, according to approved Mass General Brigham policies for data sharing. Investigators from other sites will be able to request the data and will be required to complete a data use agreement that ensures that all local IRB requirements are met before using the data, that they will not attempt to identify any data in the dataset, and that they will not share the data set with anyone outside their project team.

We will also make information necessary to interpret the data, such as study protocols, data dictionaries, and survey tools available to interested investigators.

After the primary manuscripts are published, the MGH investigators will post the data and supporting materials in an open access service such as, ICPSR (<https://www.icpsr.umich.edu/icpsrweb/>). On ICPSR, individuals must register and agree to ICPSR's Responsible Use statement prior to accessing datasets. Additionally, before a dataset is made available for access, ICPSR completes a detailed review of all datasets to assess disclosure risk. If necessary, ICPSR modifies data to reduce disclosure risk or limits access to datasets for which modifying the data would substantially limit their utility or the risk of disclosure remains

high. No information that contains identifiers or that could be used to link an individual to the data will be included in the de-identified data set.

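### Cheap improvement: the one-way ANOVA of SDM Process scores by main decision has no stated variance check; Welch's ANOVA, with care over very small groups, would close the gap

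*Combined protocol and SAP*

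**What the plan says.** All analysis text is in the combined protocol and SAP, under Statistical methods.

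- **Main decision.** "Using a one-way ANOVA we tested for differences in Pediatric SDM Process scores by main decisions". The checks listed for the scale just before this are coverage of the score range, normality, and floor or ceiling effects. Equality of variance is not among them, and no unequal-variance form is named.
- **Hypothesis 1.** Respondents with and without a top SURE score are compared by Welch's two-sample t-test, "since Pediatric SDM Process scores showed significant heterogeneity when examined for SURE groups".
- **Hypothesis 3.** "ANOVA determined if there were differences in Pediatric SDM Process scores by who made the decision". Variance is again not mentioned.
- **The score.** Under Outcomes, "a total score between 0 and 4 was calculated", and "Participants with missing answers were not given a Pediatric SDM Process score".
- **The groups.** Under Survey protocol, respondents name their own main decision, so the design does not fix group sizes. Under Sample, "Participants were caregivers (n=498) of children (aged 5-13) diagnosed with ADHD". The number scored may be lower because of the missing-answer rule.

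Table 1, cited for the main-decision item, is not in the text available for this review. Its absence is not held against the plan.

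**The concern.** The plan treats unequal spread of this score as a reason to change the test in one comparison, and says nothing about spread in two others that use the same score. The score is bounded, so spread tends to shrink in groups whose mean lies near a limit. Unequal variances are therefore plausible in other groupings too. Self-chosen categories also need not be balanced.

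The ordinary F test pools the within-group variances, weighted by group size. When both sizes and variances differ, it rejects too often if the smaller groups are the more variable, and too seldom if they are the less variable. The result could be a false statement that SDM differs by type of decision, or a missed difference. Either would colour the description of how the scale performs, which is the study's primary purpose.

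**Working it through.** **1. Inputs.** From the documents: N = 498 and a score range of 0 to 4. The 5% level is stated only for the knowledge comparison; it is assumed here. The number of main-decision groups, their sizes and their SDs are also assumptions, because the documents give none.

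**2. The plan's own figure.** The only sample-size figure is "about 0.25SD at 0.05 significance with 80% power would require 250 per group", for knowledge. With two-sided testing, n = 2(1.960 + 0.842)²/0.25² = 15.70/0.0625 = 251.2, so 252 per group, which agrees with 250. It has no bearing on the ANOVA.

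**3. Direction of the error.** With equal true means, k groups of size n_i and variance s_i²:

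- expected between-group mean square = Σ(1 − n_i/N)s_i² / (k − 1)
- expected within-group mean square = Σ(n_i − 1)s_i² / (N − k)

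Take assumed groups of 250/120/80/48 and SDs rising evenly from 1 to 1.5 (variances 1, 1.361, 1.778, 2.25).

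- Smaller groups more variable: between = (0.498 + 1.033 + 1.492 + 2.033)/3 = 1.685; within = (249 + 161.97 + 140.44 + 105.75)/494 = 1.330; ratio 1.27, so F runs high.
- Order of SDs reversed: between = (1.121 + 1.349 + 1.143 + 0.904)/3 = 1.505; within = (560.25 + 211.56 + 107.53 + 47)/494 = 1.875; ratio 0.80, so F runs low.
- Groups of 125/125/124/124 with the same SDs: 1.598/1.596 = 1.00, so there is almost no shift.

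**4. Size of the error.** Null simulation with normal scores, 20,000 runs per setting, SDs evenly spaced between the extremes. Entries are rejection rates of the ordinary ANOVA at nominal 5%.

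| Assumed groups | Largest/smallest SD | Smaller groups more variable | Smaller groups less variable |
|---|---|---|---|
| 250/120/80/48 | 1 | 4.9% | 4.9% |
| 250/120/80/48 | 1.25 | 7.8% | 3.3% |
| 250/120/80/48 | 1.5 | 10.5% | 2.3% |
| 300/130/68 | 1.25 | 7.9% | 2.9% |
| 300/130/68 | 1.5 | 10.2% | 2.0% |
| 350/80/40/28 | 1.5 | 14.7% | 1.4% |
| 125/125/124/124 | 1.5 | 5.4% | 5.1% |
| 125/125/124/124 | 2 | 5.7% | 5.7% |

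Welch's ANOVA stayed between about 4.6% and 5.3% in every one of these settings. A discrete 0-4 score with SDs from 0.8 to 1.2 in groups of 250/120/80/48 gave 10.4% or 2.4% for the ordinary test.

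A second set (6,000 runs each) used shares of 50/25/15/10% and 60/25/10/5% of 498. The ordinary ANOVA gave 8.6% to 10.7% when small groups were more variable, and 2.3% to 2.4% when they were less variable. Welch gave 4.8% to 5.2%.

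**5. Milder patterns.** With shares of 50/25/15/10% and SDs that differ little or do not follow group size, the ordinary ANOVA gave (10,000 runs each):

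- SDs 1/1/1.05/1.1: 6.0%
- SDs 1/1.3/1/1.1: 5.6%
- SDs 1.2/1/1.2/1: 3.9%
- SDs 1.15/1/1/1.15: 4.6%

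**6. Where Welch fails.** Every group was given the same left-skewed score distribution (assumed mean about 3.1, half-point steps, 8,000 runs each). With groups of 350/110/28/10, Welch rejected 8.1% and the ordinary ANOVA 5.2%. With 380/100/12/6 the figures were 11.8% and 5.1%; another run with cells of 6 to 12 gave Welch about 10%. Welch was sometimes undefined because a cell had zero variance.

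**The case against.** **The heterogeneity was found elsewhere.** A reader might infer that the plan found unequal variances and ignored them here. The text does not support that. It says "Pediatric SDM Process scores showed significant heterogeneity when examined for SURE groups". Variance heterogeneity belongs to a score within a given grouping. The wording is compatible with variances having been checked grouping by grouping, with Welch used only where needed, although the plan does not say so. This objection stands. What remains is that neither a check nor a fallback is stated for main decision.

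**The sizes are assumed.** The larger distortions come from SDs that rise or fall in step with group size, which is an unfavourable pattern. Step 5 and the near-equal groups show little effect. This stands too, and is why the figures are only illustrative.

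**Welch is not universally safe.** A reader might take it as a remedy whatever the group sizes prove to be. Step 6 shows otherwise, so the recommendation needs its caveat about very small groups.

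**The consequence is low.** The test comes before the validity and reliability analyses, is not a listed hypothesis and carries no threshold. That is right, and it sets the weight of the point. It does not make the test purely descriptive, since the plan says differences were tested. The same silence matters somewhat more for the ANOVA by who made the decision, which serves hypothesis 3.

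**Conclusion.** The point holds as a minor, conditional improvement. The plan applies an equal-variance ANOVA to self-chosen groups without stating a variance check, although it adapted its test for the same score across SURE groups.

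If variances and group sizes both differ, the true level could lie at about 2% to 11% against a nominal 5%. That range rests on assumed splits of 498 such as 50/25/15/10% and SD ratios of about 1.3 to 1.5. More extreme assumptions go further: 14.7% or 1.4% with groups of 350/80/40/28 at a ratio of 1.5. Near-equal groups or similar variances leave the level close to 5%.

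The documents do not show that the reported test was wrong, or in which direction it would err. The randomised knowledge comparison, the sample size, the retest reliability, and hypotheses 1 and 2 are unaffected.

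**What to change.** - Use Welch's ANOVA for SDM Process scores by main decision, and likewise for the hypothesis 3 ANOVA by who made the decision. If the ordinary ANOVA is kept, state the variance check that was made and its result.
- Report n, mean and SD of the score in each group for both comparisons, so that readers can judge balance and spread.
- Where a group is very small, combine it with another on substantive grounds, or set the ordinary F or a permutation test beside the Welch result. Neither cross-check protects against unequal variances, so a disagreement should be reported and not settled by choosing the smaller p-value.

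Games-Howell pairwise intervals are optional and not part of this fix, since the plan specifies no pairwise comparisons by main decision.

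**Cost.** The survey was fielded in February and March 2021 and the document is dated August 10, 2023, so this means re-running two tests on existing data. The price is a slight loss of power if variances are in fact equal, plus the small-group caution above.

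### Validity hypothesis 2 has its inequality reversed: r ≥ −.50 accepts a weak inverse correlation with regret and rejects a strong one

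*Combined protocol and SAP*

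**What the plan says.** The criterion stands in the combined protocol and SAP, Statistical methods, Validity Hypotheses, item 2: "Patients with higher Pediatric SDM Process scores had less regret ($r \geq -.50". The analysis paragraph after the hypotheses assigns a Pearson correlation "to determine the relationship between Pediatric SDM Process and regret" and adds no other threshold for this hypothesis.

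Three other statements fix the direction:

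- Survey protocol, on the SDM Process scale: "scores range 0-4, higher scores indicate more SDM".
- Outcomes, Decision Regret: "Response options were on a scale from 1 (definitely make same decision again) to 4 (definitely NOT make same decision again".
- Outcomes, Decision Regret, on earlier experience with the item: it "has been shown to be inversely related to the SDM Process scores for surgical decisions".

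The two neighbouring hypotheses show how the plan uses the ≥ sign. Item 1 reads "Patients with higher Pediatric SDM Process scores ($\geq .33SD$) were more likely to receive a top-score SURE score". Item 3 predicts that respondents whose decision was mainly the physician's "had lower Pediatric SDM Process scores ($\geq .33SD$) than respondents who reported" being involved. In both, ≥ introduces a minimum size of effect without a sign, and the words give the direction.

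**The concern.** Hypothesis 2 keeps the ≥ of its neighbours but attaches it to a signed number. On the signed scale, values at or above −.50 are the weaker inverse correlations, zero, and all positive correlations; the stronger inverse correlations lie below −.50. The printed threshold therefore works as a ceiling on the strength of the inverse association, where a convergent-validity hypothesis calls for a floor.

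The words about less regret exclude a zero or positive r, so the practical difficulty lies among negative values:

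- If −.50 < r < 0, both the wording and the printed number are satisfied, but the apparent minimum strength is not reached.
- If r < −.50, the wording is satisfied and the printed number is not, although this is the result that best supports the scale.

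The plan says that no gold standard for shared decision making exists and rests validity on these three hypotheses. The stake is whether one of them is reported as met or not met.

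**Working it through.** **Inputs from the document.** SDM Process score 0–4, higher meaning more shared decision making; regret item 1–4, higher meaning more regret; Pearson r; printed threshold r ≥ −.50; n = 498 caregivers (Sample section).

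**Assumptions.** The document gives no expected r, so true values of −.20, −.30, −.40 and −.60 are assumed. It also states that "Participants with missing answers were not given a Pediatric SDM Process score" but gives no count, so n = 400 and n = 300 are assumed as smaller numbers of scored respondents.

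**Step 1: sign.** More shared decision making with less regret pairs high values of one variable with low values of the other, so the predicted r is negative. The minus sign is right.

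**Step 2: the two rules side by side.**

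| r | Printed rule, r ≥ −.50 | Apparent intent, r ≤ −.50 |
|---|---|---|
| −.90 | fails | meets |
| −.70 | fails | meets |
| −.51 | fails | meets |
| −.50 | meets | meets |
| −.30 | meets | fails |
| −.10 | meets | fails |

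The rules agree only at exactly −.50. Taken without the words, the printed inequality would also admit r = 0 and any positive r.

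**Step 3: can another reading rescue the symbol?**

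- Reverse-scored regret: nothing in the document says so, and the predicted r would then be positive, making −.50 the wrong sign.
- Absolute value: the document does not use it here, and |r| ≥ −.50 is true of any correlation.
- A deliberate ceiling on strength: none is stated or explained, and items 1 and 3 use ≥ for a minimum.

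**Step 4: probability of each verdict.** By Fisher's transformation, z = atanh(r) with SE = 1/√(n − 3), so

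P(observed r ≤ −.50) = Φ{[atanh(−.50) − atanh(ρ)] / SE},

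and the printed rule has the complementary probability. Here atanh(−.50) = −0.5493. For n = 498, SE = 1/√495 = 0.0449.

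- ρ = −.40: atanh = −0.4236; (−0.5493 + 0.4236)/0.0449 = −2.80; Φ = 0.26%.
- ρ = −.60: atanh = −0.6931; (−0.5493 + 0.6931)/0.0449 = 3.20; Φ = 99.9%.

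| n | Assumed true r | Meets printed rule | Meets intended rule |
|---|---|---|---|
| 498 | −.20 or −.30 | >99.99% | <0.01% |
| 498 | −.40 | 99.7% | 0.26% |
| 498 | −.60 | 0.07% | 99.9% |
| 400 | −.40 | 99.4% | 0.61% |
| 400 | −.60 | 0.21% | 99.8% |
| 300 | −.40 | 98.5% | 1.5% |
| 300 | −.60 | 0.66% | 99.3% |

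Regret has only four levels, so the normal approximation was checked by simulation: 10,000 samples per setting, SDM score in 0.5 steps, regret cut at assumed points z = 0, 0.9 and 1.6, and the latent correlation tuned to give the target observed r. At n = 498 the printed and intended rules were met in 99.8% and 0.2% of samples for −.40, and in 0.06% and 99.9% for −.60. At n = 400 the figures were 99.4% and 0.65%, and 0.11% and 99.9%.

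**Step 5: strength.** Shared variance is r²: .20² = 4% against .50² = 25%. A result that meets the printed rule can therefore reflect far less association than the apparent minimum.

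**The case against.** The strongest reply is that this is a slip of notation whose intent is plain. Items 1 and 3 use ≥ for minimum size, item 2 says in words which way the association should go, and the Outcomes section calls the item inversely related. A sensible reader takes the criterion as an inverse correlation of at least .50, and anyone shown the observed r can judge it. The document is dated August 10, 2023, the survey was fielded in February and March 2021, and the methods are written in the past tense; nothing shows that the literal rule was applied. No overall verdict on validity is tied to passing all three hypotheses. The probabilities are complements of each other under assumed true correlations and say nothing about the r this study would find.

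Much of that is fair. The intent can be inferred, no misuse is documented, and the probabilities illustrate the reversal without predicting the result. The date also matters: a silent change made after fielding could look like a criterion moved after the fact. But the error itself remains. The surrounding words settle the sign of r; its required strength has to be inferred from the neighbouring hypotheses. A weak inverse correlation could be reported as meeting the stated criterion, and the document as written would support that report. The plan also promises its protocols to outside investigators, who would inherit the wrong rule.

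**Conclusion.** The concern holds. The criterion is wrong as written and should be fixed: the minus sign is right and the inequality is reversed. This follows from the document's own coding of the two scales and needs no assumption about the data; the probabilities alone rest on the assumed true correlations and numbers scored. That r ≤ −.50 was meant is an inference from the neighbouring hypotheses, though no other reading fits the text. The consequence is confined to how hypothesis 2 is judged and reported.

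**What to change.** In Validity Hypotheses, item 2, replace r ≥ −.50 with r ≤ −.50, or equivalently require a negative r with |r| ≥ .50. Judge the hypothesis on the observed Pearson r against that value. Report an r between −.50 and 0 as in the predicted direction but short of the threshold. A 95% confidence interval can be given for description; the plan does not make it a criterion.

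Because the document postdates the survey, the investigators should confirm the intended threshold and enter the change as a dated correction. The cost is one symbol and a note: no new data, and the same correlation is used.

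### Hypothesis 3 predicts that one group scores at least .33SD below another, but the only analysis that appears to serve it is an ANOVA across who made the decision, with no contrast named

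*Combined protocol and SAP*

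**What the plan says.** Under Validity Hypotheses, item 3 states: "Respondents who reported that their decision making process was mainly driven by the physician had lower Pediatric SDM Process scores", by at least .33SD, "than respondents who reported that they were involved and engaged in selecting treatment". That gives two groups, a direction and a size.

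The grouping comes from the Modified Control Preferences Scale in the Outcomes section. It is a single item with four options: mainly the respondent, mainly the provider, mainly someone else, and "You and the healthcare provider made the decision together".

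Statistical methods then gives one sentence on this relationship: "ANOVA determined if there were differences in Pediatric SDM Process scores by who made the decision". It does not carry the label of hypothesis 3, but it follows the analyses of hypotheses 1 and 2 and concerns the same subject. If it is not the analysis for hypothesis 3, that hypothesis has none.

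Hypothesis 1 is treated differently. Its two groups are defined by the SURE score (4 against below 4), and Welch's two-sample t-test is named.

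**The concern.** An omnibus F asks whether any of the group means differ. Hypothesis 3 asks whether one named group lies below another by a stated amount. The two questions coincide only if the ANOVA has exactly the two groups of the hypothesis, and the plan does not say so.

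Two things follow if the ANOVA has three or four groups. F can be significant because of a difference that hypothesis 3 does not concern, such as one between 'Mainly you' and the joint decision. And when hypothesis 3 is true, F spreads its sensitivity over comparisons that are not of interest.

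Separately, the comparator is not fully tied to the response options, and that choice can affect whether .33SD is reached. Hypothesis 3 is one of three validity hypotheses behind the stated aim: "The primary purpose is to examine the performance of the SDM Process scale for pediatric medical decisions".

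**Working it through.** **The plan's own figure.** None is given for hypothesis 3. The one sample size statement (250 per group for a .25SD knowledge difference) reproduces: 2 × (1.960 + 0.842)² / 0.25² gives 252 after rounding up, and 250 per group gives 79.8% power. It does not bear on hypothesis 3.

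**Inputs.** From the documents: total 498, four options, .33SD. Assumed, because the documents give no group sizes or means: 10 respondents in 'Mainly someone else', 50 in the provider group (range 25 to 100), the rest split 40:60 between 'Mainly you' and together, and equal SDs set to 1. The base case is 175 / 50 / 263 / 10 for you / provider / together / someone else. Tests are two-sided at 0.05.

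**Step 1: power when hypothesis 3 is true.** The provider group lies .33 below all others.

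- Four-group F: noncentrality = Σ nⱼ(μⱼ − weighted mean)² = 0.33² × 50 × 448/498 = 4.90. With 3 and 494 degrees of freedom, power is 43%.
- Contrast of provider against 'Mainly you' plus together: standard error = √(1/50 + 1/438) = 0.149, noncentrality = 0.33/0.149 = 2.21. With 486 degrees of freedom, power is 60%.

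| Provider n | Four-group F | Two-group contrast |
|---|---|---|
| 25 | 24% | 36% |
| 50 | 43% | 60% |
| 75 | 58% | 75% |
| 100 | 69% | 84% |

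If 'Mainly someone else' is left out, the three-group F has 49% power at provider n=50, still below 60%.

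**Step 2: F significant for another reason.** Set the provider group and 'Mainly someone else' at the involved average, and let 'Mainly you' lie g below together. Noncentrality = g² × 175 × 263/438 = 105.1 × g².

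| g (SD) | Noncentrality | F rejects | Range |
|---|---|---|---|
| .10 | 1.05 | 12% | 9–13% |
| .20 | 4.20 | 37% | 26–41% |
| .33 | 11.44 | 82% | 63–86% |

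The range covers provider n from 25 to 100, 'Mainly someone else' from 5 to 25, and a 'Mainly you' share of the involved group from 25% to 60%. These are rejection rates of F, not rates of wrong conclusions about hypothesis 3.

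**Step 3: effect of the comparator.** Suppose the provider group is exactly .33SD below together and 'Mainly you' is .20SD below together. Against the two options pooled, the difference is .33 − .20 × (share of 'Mainly you'). That is .25SD at a 40% share, .28SD at 25% and .21SD at 60%. With a .10SD gap and a 40% share it is .29SD. The threshold is met against together alone and missed against the pooled group.

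**The case against.** The strongest reply is that direction and size are already in the plan. Hypothesis 3 states both, and Statistical methods opens with descriptive results, so a reader who sets the group means beside the ANOVA can judge the prediction. This largely stands. Such a reader would not be misled by F alone. But means do not settle which groups form the comparison, and the plan names no test of that comparison.

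It is also fair that a two-group ANOVA would equal an equal-variance two-sample test, with no loss of power. That is possible, but the plan does not name two groups.

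The figures rest on assumed group sizes and means. Step 2 needs the provider group to sit at the involved average, and at a small gap the rejection rate is low. Step 3 places the provider group exactly at the threshold. They show what could happen, not what happened in these data.

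A reader might infer four stronger points that the documents do not support:

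- That none of the options is mapped. The physician-driven group plainly corresponds to the provider option, and counting 'Mainly you' and together as involved is the natural reading.
- That F's indifference to direction is a special fault. Any two-sided test rejects equally often for equal effects in opposite directions, including the Welch test for hypothesis 1.
- That silence on judging .33SD by the point estimate or a confidence limit is a gap in hypothesis 3. The same silence applies to the thresholds in hypotheses 1 and 2, and the point estimate is the plainest reading.
- That a significant F would have been reported as confirming hypothesis 3. Nothing in the documents says so.

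**Conclusion.** The point holds as a mismatch between a stated two-group prediction and the only analysis that appears to serve it. A four-group F does not test the comparison. Under the assumed groups it gives up 12 to 17 percentage points of power against the direct contrast at a true .33SD (24–69% against 36–84% over provider n of 25 to 100). It can also be significant through a difference between 'Mainly you' and together. What is undefined is limited to whether 'Mainly you' counts as involved and where 'Mainly someone else' belongs.

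The size depends on group shares that the documents do not give, on equal SDs, and on the ANOVA having more than two groups. Severity is minor to moderate. One of three validity hypotheses is affected, and the randomised comparison of knowledge is not.

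**What to change.** Make the analysis of hypothesis 3 a two-group contrast: the provider option against 'Mainly you' plus the joint decision. Report the signed standardised difference with its 95% CI against .33SD. Welch's test, as for hypothesis 1, is reasonable but not essential, because the plan reports unequal variances only for the SURE groups.

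Add one sensitivity check, provider against the joint decision only. Keep the ANOVA, with n, mean and SD for each group, as descriptive; this also shows 'Mainly someone else', which the contrast leaves out.

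Label the contrast as specified after data collection. The document is dated August 10, 2023, and "The online survey was fielded between February 2021 and March 2021".

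The cost is a few sentences and a few lines of code on data already held. The omnibus p-value would no longer be the main result for this hypothesis. The real drawback is that the grouping becomes a post-collection choice that the documents do not settle, which is why the sensitivity check is needed.
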